6.3.3 Management of RAD001 toxicities

Known Undesirable Side Effects of RAD001

Adverse events most frequently observed with RAD001 are rash, stomatitis/oral mucositis, fatigue, headache, anorexia, nausea, vomiting, diarrhea, ocular toxicity and infections. Non-infectious pneumonitis has also been observed. Overall, the most frequently observed laboratory abnormalities include neutropenia, thrombocytopenia, hypercholesterolemia, and/or hypertriglyceridemia. The majority of these AEs have been of mild to moderate severity (CTC grade 1-2).

Table 6-2 Criteria for dose-modification in case of suspected RAD001 toxicity and re-initiation of RAD001 treatment

Toxicity	Actions
Non-hematological toxicity Grade 2 (except pneumonitis, refer to Table 6.3)	If the toxicity is tolerable to the patient, maintain the same dose. If the toxicity is intolerable to patient, interrupt RAD001 until recovery to grade \leq 1. Then reintroduce RAD001 at same dose. If event returns to grade 2, interrupt RAD001 until recovery to grade \leq 1. Then reintroduce RAD001 at the lower dose level.
Grade 3 (except hyperlipidemia)	Interrupt RAD001 until recovery to grade \leq 1. Then reintroduce RAD001 at the lower dose level. For pneumonitis, consider the use of a short course of corticosteroids (see table 6.3).
Grade 3 hyperlipidemia (hypercholesterolemia and/or hypertriglyceridemia)	Should be managed using standard medical therapies.
Grade 4	Discontinue RAD001.
Hematological toxicity Grade 2 Thrombocytopenia (platelets $<$ 75, \geq 50x10 ⁹ /L)	Interrupt RAD001 until recovery to grade \leq 1 (platelets \geq 75x10 ⁹ /L). Then reintroduce RAD001 at initial dose. If thrombocytopenia again returns to grade 2, interrupt RAD001 until recovery to grade \leq 1. Then reintroduce RAD001 at the lower dose level.
Grade 3 Thrombocytopenia (platelets $<$ 50, \geq 25x10 ⁹ /L)	Interrupt RAD001 until recovery to grade \leq 1 (platelets \geq 75x10 ⁹ /L). Then resume RAD001 at one dose level lower. If grade 3 thrombocytopenia recurs, discontinue RAD001.
Grade 4 Thrombocytopenia (platelets $<$ 25x10 ⁹ /L)	Discontinue RAD001.

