Grade 3 Neutropenia (neutrophils $< 1, \geq 0.5 \times 10^9/L$)	Interrupt RAD001 until recovery to grade ≤ 1 (neutrophils $\geq 1.5 \times 10^9/L$). Then resume RAD001 at the initial dose. If ANC again returns to Grade 3, hold RAD001 until the ANC $\geq 1.5 \times 10^9/L$. Then resume RAD001 dosing at the lower dose level. Discontinue patient from study therapy for a third episode of grade 3 neutropenia.
Grade 4 Neutropenia (neutrophils $< 0.5 \times 10^9/L$)	Interrupt RAD001 until recovery to grade ≤ 1 (neutrophils $\geq 1.5 \times 10^9/L$). Then resume RAD001 at the lower dose level. If grade 3 or grade 4 neutropenia occurs despite this dose reduction, discontinue RAD001.
Grade 3 febrile neutropenia (not life-threatening)	Interrupt RAD001 until resolution of fever and neutropenia to grade ≤ 1 . Hold further RAD001 until the ANC $\geq 1,500/mm^3$ and fever has resolved. Then resume RAD001 at the lower dose level. If febrile neutropenia recurs, discontinue RAD001.
Grade 4 febrile neutropenia (life-threatening)	Discontinue RAD001.
Any hematological or non-hematological toxicity requiring interruption for ≥ 3 weeks	Discontinue RAD001.

Monitoring of RAD001 suspected toxicities

Patients whose treatment is interrupted or permanently discontinued due to an adverse event or abnormal laboratory value suspected to be related to RAD001 must be followed at least weekly via telephone until the adverse event or abnormal laboratory value resolves or returns to grade 1. If a patient requires a dose delay of > 21 days from the intended day of the next scheduled dose, then the patient must be discontinued from the study.

Management of stomatitis/oral mucositis/mouth ulcers

Stomatitis/oral mucositis/mouth ulcers due to RAD001 should be treated using local supportive care. Please note that investigators in earlier trials have described the oral toxicities associated with RAD001 as mouth ulcers, rather than mucositis or stomatitis. If your examination reveals mouth ulcers rather than a more general inflammation of the mouth, please classify the adverse event as such. Please follow the paradigm below for treatment of stomatitis/oral mucositis/mouth ulcers:

1. For mild toxicity (grade 1), use conservative measures such as **non-alcoholic mouth wash or salt water (0.9%) mouth wash** several times a day until resolution.

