7.5 Safety

7.5.1 Adverse events

An adverse event is the appearance or worsening of any undesirable sign, symptom, or medical condition occurring after date of signed informed consent even if the event is not considered to be related to study drug. Study drug includes the investigational drug under evaluation that is given during any phase of the trial. Medical conditions/diseases present before date of signed informed consent are only considered adverse events if they worsen

after date of signed informed consent. Abnormal laboratory values or test results constitute adverse events only if they induce clinical signs or symptoms, are considered clinically significant, or require therapy (e.g. any hematologic abnormality that requires transfusion or cytokine treatment). In addition, abnormal laboratory values that cause study discontinuation or constitutes in and of itself a Serious Adverse Event (SAE) should be recorded on the Adverse Events CRF.

Adverse events will be assessed according to the Common Terminology Criteria for Adverse Events (CTCAE) version 3.0 (<http://ctep.cancer.gov/forms/CTCAEv3.pdf>). If CTCAE grading does not exist for an adverse event, the severity of mild, moderate, severe, and life-threatening, OR grades 1 – 4, will be used. **CTCAE grade 5 (death) will not be used in this study; rather, this information will be collected in the End of Treatment or Survival Information CRF page.** Adverse event monitoring should be continued for at least 4 weeks following the last dose of study drug.

The occurrence of adverse events should be sought by non-directive questioning of the patient at each visit during the study. Adverse events also may be detected when they are volunteered by the patient during or between visits or through physical examination, laboratory test, or other assessments. As far as possible, each adverse event should be evaluated to determine:

1. the severity grade (CTCAE Grade 1 – 4) or mild, moderate, severe, life-threatening if CTCAE grading does not exist for an adverse event,
2. its relationship to the study drug(s) (suspected/not suspected),
3. its duration (start and end dates or if continuing at final exam),
4. action taken (no action taken; study drug dosage adjusted/temporarily interrupted; study drug permanently discontinued due to this adverse event; concomitant medication taken; non-drug therapy given; hospitalization/prolonged hospitalization), and

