1.3 Treatments (study drug, rescue medication, other concomitant therapies, compliance)

Study drug and concomitant therapies were analyzed for the safety set.

Study drug

Duration of exposure to study drug was defined as the time from start of treatment to the last end date documented in the Study Drug Administration CRF. Duration of exposure was summarized descriptively.

Mean daily doses of study drug were calculated including and excluding zero doses for periods of temporary interruption of treatment regardless of whether this was due to safety reasons or patients' non-compliance. Mean daily doses were summarized descriptively.

The number of dose changes/patients with dose changes (including temporary dose interruption) was presented by reason for dose change by frequency distribution. Permanent treatment discontinuations were analyzed by frequencies.

Concomitant medications

Concomitant medications were coded according to WHO-DRL and summarized by ATC class and preferred term using frequency tables.

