1.5.2.1 Adverse events

Adverse events (AE) were summarized by presenting the number and percentage of patients having any adverse event, having an adverse event in each body system and having each individual adverse event. Furthermore, the incidence of AE was summarized by maximum severity, for AE with suspected drug relation, for serious AE, for AE leading to permanent discontinuation of study drug, and for significant AE. As significant (S)AE were defined those (S)AE who

- were suspected to be drug related,
- lead to dose adjustment or temporary interruption,
- lead to permanent discontinuation,
- required concomitant medication/non-drug therapy, and
- Deaths

Any other information collected (e.g. severity or relatedness to study medication) was listed as appropriate.

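### Section 7.5.1 does not make dose interruption or reduction a trigger for recording a laboratory value as an AE, so some cytopenias that change dosing under Table 6-2 can be missing from the AE tables

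*Protocol*

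**What the plan says.** **Dosing.** Protocol 6.3.3, Table 6-2, ties dosing to platelet and neutrophil thresholds with no condition on symptoms or treatment. For a second grade 2 thrombocytopenia: "If thrombocytopenia again returns to grade 2, interrupt RAD001 until recovery to grade" 1 or lower, then restart at the lower level. For grade 3 neutropenia, after the first interruption: "Then resume RAD001 at the initial dose. If ANC again returns to Grade 3, hold RAD001 until the ANC" has recovered, then restart lower.

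**AE recording.** Protocol 7.5.1 states the main rule: "Abnormal laboratory values or test results constitute adverse events only if they induce clinical signs or symptoms, are considered clinically significant, or require therapy". Its hematological example of the therapy trigger is "any hematologic abnormality that requires transfusion or cytokine treatment". It then adds that "abnormal laboratory values that cause study discontinuation or constitutes in and of itself a Serious Adverse Event (SAE) should be recorded" on the AE form.

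**Reporting.** SAP 1.5.2.1 defines significant AEs to include those that "lead to dose adjustment or temporary interruption". SAP 1.3 says that the number of dose changes, and of patients with them, "was presented by reason for dose change by frequency distribution". SAP 1.5.2.2 describes summary statistics of raw laboratory values and of changes from baseline by visit, and says notable values were not analyzed because the protocol defined no notable ranges. Protocol 10.5.2.2 had also planned shift tables from baseline to the most extreme later value. SAP 1.5.2.2 does not mention them.

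**The concern.** The protocol treats certain counts as serious enough to stop or reduce the drug, but its recording rule does not treat that action as a reason to enter an AE. Where no other trigger applies, the entry rests on a judgement of clinical significance that the protocol does not define and that sites may make differently.

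Tolerability and safety is the first secondary objective, and protocol 6.3.3 names neutropenia and thrombocytopenia among the most frequent laboratory abnormalities. There is no control arm against which a low rate would look odd. SAP 1.5.2 rests safety mainly on AE frequency and on the number of laboratory values outside pre-determined ranges. If the AE route is incomplete, the laboratory route has to compensate, and SAP 1.5.2.2 has narrowed it.

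**Working it through.** The documents give no figure to reproduce, so the check sets Table 6-2 against 7.5.1 row by row.

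Triggers in 7.5.1: (a) signs or symptoms; (b) considered clinically significant; (c) requires therapy; (d) causes study discontinuation; (e) is itself an SAE.

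| Situation in Table 6-2 | Dosing action | Trigger met by the row itself | AE entry assured? |
|---|---|---|---|
| Grade 2 thrombocytopenia, first | Interruption | None | No, rests on (b) |
| Grade 2 thrombocytopenia, recurrent | Interruption, lower level | None | No, rests on (b) |
| Grade 3 thrombocytopenia, first | Interruption, lower level | None | No, rests on (b) |
| Grade 3 neutropenia, first | Interruption | None | No, rests on (b) |
| Grade 3 neutropenia, second | Interruption, lower level | None | No, rests on (b) |
| Grade 4 neutropenia, first | Interruption, lower level | None | No, rests on (b) |
| Grade 4 thrombocytopenia; recurrent grade 3 thrombocytopenia; third grade 3 neutropenia; grade 3 or 4 neutropenia after a reduction for grade 4; interruption of 3 weeks or more | Discontinuation | (d), because protocol 5.2 makes stopping study drug a reason for withdrawal | Yes |
| Febrile neutropenia | Interruption and lower level, or discontinuation | (a), fever | Yes |

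An episode in the first six rows is also recorded if it happens to be symptomatic, treated or an SAE. The gap is what remains: asymptomatic, untreated, non-discontinuing cytopenia that the investigator does not consider clinically significant.

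**Does trigger (b) close the gap by implication?** Not clearly. If every count that alters dosing were clinically significant by definition, the separate discontinuation trigger would be redundant. Protocol 6.3.3 and 6.3.4 also name an adverse event and an abnormal laboratory value as alternative reasons for interrupting the drug. The action-taken item in 7.5.1 does include dose adjustment and interruption, but it describes an AE already entered and does not create one.

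**Would another planned output show these episodes?**

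1. The SAP 1.5.2.1 count of AEs leading to dose adjustment or interruption needs an AE record.
2. The SAP 1.3 table counts dose changes by reason. The text mentions neither laboratory test nor grade, and the documents do not list the reason codes.
3. The SAP 1.5.2.2 summaries are by visit. SAP section 1 adds minimum and maximum, so an extreme count would be visible, but not the number of patients at each grade or any link to dosing.
4. The protocol 10.5.2.2 shift tables would show each patient's worst value by range category, though not whether dosing changed. The SAP does not carry them over.

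**Size.** Let k be the number of patients in an arm with such an episode and u the share judged not clinically significant. The AE-based count is then k(1 − u). The documents give neither k nor u. What follows from the sample sizes is the weight of one missed patient: 1/36 = 2.8 percentage points in arm I, 1/24 = 4.2 in arm II (both at planned size), and 1/8 = 12.5 in arm III with the 8 enrolled patients reported in protocol section 10.

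**The case against.** The best defence is that the protocol's own language points towards AE status. Section 6.3.3 lists neutropenia and thrombocytopenia and then refers to the listed events as AEs. Table 6-2 applies to suspected drug toxicity, 6.3.2 grades toxicity by the CTC for adverse events, and 6.3.3 requires at least weekly telephone contact after an interruption. An investigator who attributes a count to the drug, holds treatment and telephones weekly would often call it clinically significant. That stands as a reason to expect many of these episodes to be recorded. It does not make recording mandatory, because 7.5.1 is the governing rule and is worded as a closed list.

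A reader might infer that 7.5.1 records laboratory values only for study discontinuation or an SAE. It does not. Those two are additions, and the symptom and therapy triggers are equally mandatory.

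A reader might also infer that these episodes vanish from all reporting. They do not. Dose changes go on the CRF and are tabulated by reason, and the SAP is silent on shift tables rather than expressly cancelling them; what it expressly drops is the notable-value analysis.

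The separate codes for adverse events and abnormal laboratory values in protocol 6.3.6 are weak support for the point, since they are reasons for leaving the study and not for changing dose.

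Finally, enrollment is complete and two patients remained on drug on 23 July 2013, so a new sentence in 7.5.1 would reach about two patients. That is correct, and it puts most of the value in the retrospective derivation.

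**Conclusion.** The point holds within limits. The six situations in the first rows of the comparison change dosing without assuring an AE entry. The SAP count of AEs leading to dose adjustment or interruption can therefore fall short for thrombocytopenia and neutropenia, and no summary table described in the SAP reliably supplies the missing episodes by grade. Rows ending in discontinuation and febrile neutropenia are already covered.

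The bias runs one way, towards under-counting. Its size is unknown and could be nil if investigators treated every such count as clinically significant. The documents support no claim about how many episodes were missed. The conclusion assumes that 7.5.1 was applied as written and that no CRF instruction or table shell outside these documents closes the gap. This is an inexpensive improvement to a safety output. It does not affect the primary analysis and does not call any dosing rule into question.

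**What to change.** 1. **Protocol 7.5.1.** Reconcile it with Table 6-2 by extending the sentence that adds discontinuation and SAE, so that it also covers laboratory values leading to interruption or reduction of study drug, recorded with CTCAE grade. Table 6-2 stays as it is.
2. **SAP 1.5.2.1, for patients already treated.** Add one table that matches CTCAE-graded platelet and neutrophil values to interruption and reduction dates in the dosing record. Use the dose-change reason code only if the CRF has one. Report the result beside the AE-based count, not in place of it, so that the difference can be seen.
3. **SAP 1.5.2.2.** Keep the protocol's baseline-to-worst shift tables for hematology.

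The cost is one sentence, one extra derivation and tables already planned in the protocol. The reported rate of dose-modifying cytopenia may rise slightly. The derivation uses hematology and dosing data that the protocol already collects. It depends on the triggering counts, including any taken between visits, being in the database, and this should be checked first.

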As on 23 July 2013, one patient in arm II and one patient in arm III are ongoing and receive study drug. To ensure drug supply to both patients with RAD001 (everolimus), this amendment implements the use of Afinitor® (everolimus) as study drug.

Changes to the protocol

Additions to the study protocol are shown in red and deletions are shown in ~~strike out mode~~. Comments and instructions for changes are shown in *italics*.

Changes to Section 6 Treatment

The section was amended as follows:

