1.3.3 RAD001 Phase I Studies

RAD001 has been evaluated in phase I studies involving 147 patients with advanced cancers using both a weekly regimen (up to 70mg/wk) and a daily regimen (10mg/d) [Investigators' Brochure, 2006]. The most frequent adverse drug reactions in the oncology setting have been rash, stomatitis, fatigue and, to a lesser extent, gastrointestinal disorders (nausea, anorexia, diarrhea, vomiting) and headache. The adverse events are mild-moderate (CTC grade 1-2) in the majority of patients. Severe (grade 3), suspected drug-related, dose-limiting events occurred in 19% of patients, mainly stomatitis (often aphthous ulcers), and occasionally severe fatigue, hyperglycemia and neutropenia. Reduced blood counts, hyperlipidemia (mainly hypercholesterolemia) and hyperglycemia are relatively frequent laboratory findings. Infections have not been frequent.

The dose and schedule of 10mg p.o. q.d. has been selected for most phase II studies based on assessment of both pharmacodynamic and safety studies. Molecular pharmacodynamic studies using immunohistochemistry assays on tumor biopsies have shown target inhibition at both daily dosage (5-10mg) and weekly dosage (50-70mg) with satisfactory tolerability in most patients.

Conventional cytotoxic agents were empirically evaluated in *in vitro* and *in vivo* pharmacology studies as combination partners for RAD001 and have shown that RAD001 is additive or synergistic in combination with other anticancer agents, including cytotoxics and other signal transduction inhibitors (STIs) as well as endocrine therapy. In many cases, a potentiation of cell death by the drug combination was observed. RAD001 has also been evaluated in several phase I studies in combination with other anticancer drugs. Interactions have required dose reduction of RAD001 when given in combination with some drugs (e.g. Gleevec, Xeloda) but not others (e.g. paclitaxel, letrozole). Please refer to Investigator Brochure for more information.

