5.2 Premature patient withdrawal

Patients must be withdrawn from the study for any of the following reasons:

- Withdrawal of informed consent
- Pregnancy
- Study drug discontinuation
- Progression of tumor
- Unacceptable toxicity
- Patients also should be withdrawn at any time if the investigator concludes that it would be in the patient's best interest for any reason.

The reason for premature patient withdrawal from the study must be recorded on the Study Completion CRF.

Protocol violations should not lead to patient withdrawal unless they indicate a significant risk to the patient's safety.

Patients may voluntarily withdraw from the study for any reason at any time. They may be considered withdrawn if they state an intention to withdraw, or fail to return for visits, or become lost to follow up for any other reason.

For patients who are lost to follow-up (i.e. those patients whose status is unclear because they fail to appear for study visits without stating an intention to withdraw), the investigator should show "due diligence" by documenting in the source documents steps taken to contact the patient, e.g. dates of telephone calls, registered letters, etc.

Patients who are prematurely withdrawn from the core study will be replaced by an equal number of newly enrolled patients.

6 Treatment

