6.3 Treating the patient

6.3.1 Instructions for prescribing and taking the study drug

RAD001 will be dispensed by the study center personnel on an outpatient basis. Patients will be provided with an adequate supply of RAD001 for self-administration at home.

RAD0001 will be dosed starting on Week 1 Day 1. Patients will be instructed to take two tablets of RAD001 orally with a glass of water, once daily at the same time each day, in a fasting state or after no more than a light, fat-free meal. If vomiting occurs, no attempt should be made to replace the vomited dose. Patients should be requested to bring their unused medication, including the empty blister packs, to the clinic at each visit. Compliance should be verified by the investigator's staff through counting the number of tablets consumed between visits.

The investigator (or his/her designee) will document dosage administration and all dose changes during the study in the CRF. The site must maintain an overall drug accountability log for the study, as well as individual accountability records for each patient. The dose, amount dispensed, amount received, and amount remaining unused must be recorded in the source document. Drug accountability will be noted by the field monitor during site visits and at the completion of the study. The patient will be asked to return all unused RAD001 at the end of study treatment.

Patients will be treated with RAD001 until progression of tumor, the occurrence of unacceptable toxicity, or until the investigator or patient decides that continuation is not in the best interest of the patient. Interruption for toxicity should follow the instructions in Table 6.2.

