6.3.2 RAD001 dose adjustments

For patients who are unable to tolerate the protocol-specified RAD001 dosing schedule, dose-adjustment guidelines are given below. Three RAD001 dose levels are defined for dose adjustment: 10mg daily, 5mg daily, and 5mg every other day. (Table – 1)

Table 6-1 RAD001 Dose levels for dose adjustment

Dose level	Dose and schedule
0 (starting dose)	10mg daily
Decrease 1 dose level	5mg daily
Decrease 2 dose levels	5mg every other day

Toxicity will be assessed using the NCI-CTC for Adverse Events, version 3.0 (CTCAE v3.0,

(<http://ctep.cancer.gov/forms/CTCAEv3.pdf>).

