****This list of clinically relevant drug interactions is updated as of December 02, 2009****

6.3.6 Study drug discontinuation

Study drug must be discontinued for a given patient if the investigator determines that continuing it would result in a significant safety risk for that patient. Patients who, in the opinion of the investigator, require alternative medical therapy, will be discontinued from the study. Patients with a progression will be discontinued from the study. Patients who become pregnant during the study must be withdrawn. If the treatment has to be interrupted for more than 21 consecutive days for any reason, the patient will be discontinued from the study unless otherwise discussed with the study coordinator. In case of patient's discontinuation, the end of study evaluation will be completed as soon as possible. End of study evaluations will include adverse events, concomitant medications and therapies, physical examination, vital signs, ECOG performance status, biochemistry, hematology and tumor measurement.

Patients who discontinue prematurely due to significant AE should continue to be followed-up until resolution of the AE, and the relevant sections of the CRF should be completed as appropriate. Patients who are discontinued due to clinically significant abnormalities in clinical laboratory results should continue to be evaluated until the abnormality resolves or is judged to be permanent.

It will be documented whether or not each patient completed the clinical study. If, for any patient, the study treatment was discontinued the reason will be recorded. Reasons that a patient may discontinue participation in a clinical study are considered to constitute one of the following:

1. Adverse event(s)
2. Abnormal laboratory value(s)
3. Abnormal test procedure result(s)
4. Unsatisfactory therapeutic effect
5. Subject's condition no longer requires study treatment

6. Protocol violation which affect the safety of the patient
7. Subject withdraws consent
8. Lost to follow-up
9. Administrative problems
10. Death

Progressive disease is defined as unsatisfactory therapeutic effect.

For patients who are lost to follow-up, the investigator should show “due diligence” by documenting in the source documents steps taken to contact the patient, e.g. dates of telephone calls, registered letters, etc.

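### After two grade 3 neutropenia episodes, Table 6-2 read row by row stops RAD001 for a third plain grade 3 episode but lets it resume after a first grade 4 or first grade 3 febrile episode

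*Protocol*

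**What the plan says.** Protocol 6.3.2 sets the dose ladder: "Three RAD001 dose levels are defined for dose adjustment: 10mg daily, 5mg daily, and 5mg every other day". Table 6-2 in 6.3.3 then gives each type of neutropenia its own row.

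- **Grade 3** (neutrophils below 1 and at least 0.5 x 10^9/L): after recovery, the first episode resumes at the initial dose and the second at the lower level. For the next: "Discontinue patient from study therapy for a third episode of grade 3 neutropenia".
- **Grade 4** (below 0.5 x 10^9/L): interrupt until at least 1.5 x 10^9/L, then resume at the lower level. The row ends: "If grade 3 or grade 4 neutropenia occurs despite this dose reduction, discontinue RAD001".
- **Grade 3 febrile, not life-threatening**: interrupt until fever and counts recover, then resume at the lower level. Stop if febrile neutropenia recurs.
- **Grade 4 febrile, life-threatening**: stop.

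A further row stops RAD001 when any toxicity needs an interruption of 3 weeks or more. Outside the table, 5.2 and 6.3.1 end treatment for unacceptable toxicity, and 6.3.6 adds: "Study drug must be discontinued for a given patient if the investigator determines that continuing it would result in a significant safety risk".

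**The concern.** The grade 3 row counts only grade 3 episodes. The grade 4 row and the grade 3 febrile row do not mention earlier plain grade 3 episodes or reductions already made for them. For a patient who has used up the allowance in the grade 3 row, the three rows therefore give actions that run against severity. A neutrophil count of 0.6 x 10^9/L without fever ends treatment. A count of 0.4, or a first grade 3 episode with fever, permits re-exposure.

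What is at stake is dosing safety and consistency. Two sites could treat the same patient differently. Under the literal reading, a patient who has just had a third and worst episode on an already reduced dose is given the drug again.

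**Working it through.** No figure in the plan has to be reproduced. The check traces Table 6-2 on the dose ladder in Table 6-1, starting at 10 mg daily with no dose change for any other toxicity. Write 3 for plain grade 3, 4 for non-febrile grade 4 and F for grade 3 febrile neutropenia.

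**Step 1. Reach the branch point.** The first 3 resumes at 10 mg daily and the second 3 resumes at 5 mg daily. One level remains: 5 mg every other day, which averages 5 / 2 = 2.5 mg per day, or 2.5 / 10 = 25% of the starting dose. An instruction to go one level down can therefore still be carried out.

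**Step 2. Compare the possible third episodes, each row read on its own.**

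| Third episode | Row that names it | Action |
|---|---|---|
| 3 | Grade 3 | Stop |
| 4 (first) | Grade 4 | Resume at 5 mg every other day |
| F (first) | Grade 3 febrile | Resume at 5 mg every other day |
| Grade 4 febrile | Grade 4 febrile | Stop |

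The second and third lines are the inversions.

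**Step 3. Count episodes at the stop, non-febrile rows only.**

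| Path | Literal reading | If an earlier reduction counts in the grade 4 row |
|---|---|---|
| 4-3, 4-4 | stops at 2 | stops at 2 |
| 3-3-3, 3-4-3, 3-4-4 | stops at 3 | stops at 3 |
| 3-3-4 | resumes; 3-3-4-3 and 3-3-4-4 stop at 4 | stops at 3 |

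The difference is 4 - 3 = 1 possible extra severe episode, on this one branch. These are counts of paths, not probabilities.

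**Step 4. Add the febrile row.** After 3-3-F the patient is on 5 mg every other day. A further plain grade 3 is the third of its kind and stops the drug. A febrile recurrence also stops it. Either stop comes at the fourth episode. A grade 4 episode at that point calls for a lower level, and Table 6-1 has none, so the row cannot be carried out as written.

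**Step 5. Look for a rule that closes the gap.** The general grade 4 instruction to stop sits under non-hematological toxicity. The grade 4 febrile row covers life-threatening febrile cases only. The 3-week rule depends on how long recovery takes. None expressly settles 3-3-4 or 3-3-F. The thrombocytopenia rows do keep the order of severity at the top: recurrent grade 3 stops and any grade 4 stops.

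**The case against.** **The text has benign readings.** The reduction mentioned at the end of the grade 4 row could include the earlier step to 5 mg daily. A grade 4 event could also be counted as the third episode. Either would stop the drug after 3-3-4. Both readings are open, but neither is written. The reduction named in "If grade 3 or grade 4 neutropenia occurs despite this dose reduction, discontinue RAD001" follows directly on the grade 4 row's own reduction. That row also names both grades, whereas the grade 3 row names one, so a site cannot assume that the grades are pooled. Neither reading, as it stands, alters the instruction to resume in the febrile row.

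**The table counts row by row throughout.** Other mixed sequences are left open too, and 6.3.2 calls these rules guidelines. That is fair, and it argues against giving the point much weight. But leaving a sequence open differs from stating actions that run against severity.

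**Backstops exist and are mandatory in form.** Section 5.2 lists unacceptable toxicity under "Patients must be withdrawn from the study for any of the following reasons", and the safety stop in 6.3.6 is also an obligation. These limit harm substantially. They rest on judgement, and the table's remaining stops need a long interruption or a further event, so the conflict between rows remains.

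**Stronger readings to resist.** A reader might infer that the protocol compels re-exposure. It does not, given the alternative readings and the backstops. A reader might infer an effect on the trial's results. The response definition, the sample sizes and the decision rules do not depend on these rows. A reader might also take the two patients on drug at Amendment 7 as a cap on everyone ever exposed to the rule. They are not: earlier patients may have been dosed under the same rows, and the documents do not show when the rows were introduced.

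**Conclusion.** The point holds as an inconsistency in the dosing rules for third episodes after two plain grade 3 episodes. Read row by row, a first grade 4 or a first grade 3 febrile episode gets a milder action than a third plain grade 3. On the non-febrile branch the cost is one possible extra severe episode.

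This rests on a start at 10 mg daily, no reduction for another toxicity, recovery in under 3 weeks, and an investigator who sees no overriding safety risk. It also takes a febrile episode as belonging to its own row and not as a third grade 3 episode, which the table does not address.

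The sequence needs three separate severe episodes and is expected to be rare. The documents give no rate. On severe neutropenia in phase I, Protocol 1.3.3 says only "and occasionally severe fatigue, hyperglycemia and neutropenia". No endpoint, sample size or error rate is affected. Severity is minor: a cheap improvement for patient safety.

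**What to change.** Add one overriding rule to all the neutropenia rows of Table 6-2:

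*Discontinue RAD001 for a third episode of neutropenia of grade 3 or 4, with or without fever, all episodes counted together, whichever row would otherwise apply; any earlier stop in a row still applies.*

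With this rule 3-3-3, 3-3-4 and 3-3-F all stop at the third episode, and the step below the lowest dose after 3-3-F no longer arises. The existing stops at 4-3 and 4-4, at a febrile recurrence and at grade 4 febrile neutropenia are unchanged. Editing only the plain grade 3 and grade 4 rows would not be enough, because the febrile row would still say to resume.

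The cost is one sentence, with no added visits, assessments or patients and no change to the analysis. The downside is that a few patients stop one episode earlier than under the literal reading, which is what the protocol already requires for a less severe third event. Reach is limited. The Amendment 7 rationale reports enrollment complete and, as of 23 July 2013, "one patient in arm II and one patient in arm III are ongoing and receive study drug". A future amendment would therefore reach only patients still on drug. A clarification to the sites treating them would serve, and the wording should be corrected before the table is used again.
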